3.2.10. Hemophilia Joint Health Score (HJHS)

Joint assessments will be performed using the HJHS version 2.1 to evaluate joint total (swelling, duration of swelling, muscle atrophy, crepitus on motion, flexion loss, extension loss, joint pain, and strength) and global gait scores. HJHS data will be collected at Baseline, Week 24, Week 52, Week 104, Week 156, Week 208, and Week 260 or Early Discontinuation Visit. If the HJHS cannot be performed at Week 24 and/or Week 52, it is recommended that it be performed at the next subsequent on-site visit or unplanned visit. Change in joint health score measured by the HJHS instrument will be summarized by visit.

Six joints (left ankle [LA], right ankle [RA], left elbow [LE], right elbow [RE], left knee [LK], right knee [RK]) will be scored on a scale from 0 to 20 according to the following criteria: duration of swelling, muscle atrophy, crepitus on motion, flexion loss, extension loss, instability, joint pain, and strength. Gait will be scored on a scale from 0 to 4 based on walking, stairs, running, hopping on one leg. The total score will be the sum of scores from all 6 joints plus the gait score (range from 0 to 124). A higher total score will indicate more severe joint damage. The baseline assessment is based on the latest evaluation prior to PF-07055480 infusion, which is measured during the baseline period of this study.

The HJHS Total Score, ranging from 0 to 124, is obtained using the following formula:

$$\text{HJHS Total Score} = \frac{\text{total score of evaluated items (excluding not evaluable items)}}{\text{possible maximum total score of evaluated items (excluding not evaluable items)}} \times 124$$

HJHS Total Score will not be derived if >20% of items are missing (including not evaluable [NE] items).

Note: there are 49 individual items to score, therefore 10 or more missing or NE will result in the total score not being calculated.

The derivation for the CSR reporting will be done ***solely based on 49 item scores***. That is, if investigator sites input any total score from work sheet, those 'calculated' inputs will NOT be used for derivation of the total score for the CSR reporting purpose.

3.2.11. Patient-Reported Outcome (PRO) Assessments

The PRO questionnaires should be completed (at Baseline, Week 12, Week 24, Week 52, Week 104, Week 156, Week 208 and Week 260 or early discontinuation visit) in accordance with the SoA during the scheduled site visits using a tablet device that will be provided to each site (or to the home-health vendor as applicable). Every effort should be made to conduct the PROs according to the protocol specified timepoints; however, if not feasible, baseline PROs have to be conducted any time prior to start of infusion on Day 1, postinfusion PROs at the next subsequent on-site visit or unplanned visit. At each relevant visit, the assessment questionnaires should be administered before dosing, treatment, or conversation between health care team and participants about their health condition. Participants should complete the questionnaires in a quiet area within the clinic (i.e., cannot be taken home) or at home (provided by the home-health vendor) and without help or interaction from family members or other caregivers. Spouses, family members, visitors, or health care team members should not assist the participant in answering questionnaires.

3.2.11.1. Haemophilia Quality of Life Questionnaire for Adults (Haem-A-QoL)

The Haem-A-QoL is a disease specific measure of health-related quality of life in patients with hemophilia. Intended for adults, the instrument uses a 4-week recall period to assess health across 10 domains consisting of 46 items. The 10 domains and the number of items within each domain of the adult version are the following: Physical Health (5 items); Feelings (4 items); View of Self (5 items); Sports and Leisure (5 items); Work and school (4 items); Dealing with Haemophilia (3 items); Treatment (8 items); Future (5 items); Family Planning (4 items); and Partnership and Sexuality (3 items). Scores are calculated by domain and a single total score. The 10 domains of health-related quality of life within each visit window will be summarized. Missing data will not be imputed to calculate the total score and score for an individual domain. Change from baseline in individual domain scores and the total score will be summarized by visit. The baseline assessment is based on the latest evaluation prior to PF-07055480 infusion, which is measured during the baseline period of this study.

3.2.11.2. Hemophilia Activities List (HAL, Version 2)

The Hemophilia Activities List (version 2) is a multiple domain measure of the impact of hemophilia on functional abilities in adults. The 7 domains of this instrument contain 42 items in total, as follows: Lying/sitting/kneeling/standing (8 items); lower (leg) functioning (9 items); upper (arm) functioning (4 items); Transportation (3 items); Self-care (5 items); Household tasks (6 items); and Sports/Leisure (7 items). Scoring can be done by domain, components (Activities involving the Upper Extremities, Basic activities involving the Lower Extremities, and Complex activities involving the Lower Extremities) or a standardized total score.

All items are rated on a 6-point scale from 1 (impossible) to 6 (never) describing difficulty due to hemophilia in the past month. Several items allow the respondent to mark as 'not applicable'.

Selected items from five of the domains are used to create three components: upper extremity; basic lower extremity; and complex lower extremity activities.

Responses from individual items can be summed to give a score for each domain and component, and the total. Higher values indicate better quality of life, that is, higher values indicate less functional limitations in performing tasks.

The activities list also includes two sets of multiple-choice items assessing the use of adaptive and assistive devices; these items are not included in the scoring.

HAL baseline is the latest evaluation prior to PF-07055480 infusion, which is measured during the baseline preinfusion period of this study. The normalization method to derive score of domains and three components will be used to impute any missing item. Change from baseline in individual domain scores, component scores and the standardized total score will be summarized by visit.

3.3. Other Endpoints

3.3.1. Additional PRO Assessments

Additional PRO assessments implemented in this study are the HLIQ and the EQ-5D-5L. Additionally, 6 anchor items have been developed to assess change over time on the Haem-A-QoL, the HAL, and the HLIQ: three patient global impression of severity (PGIS) items and 3 patient global impression of change (PGIC) items. The 3 PGIS single item assessments will be completed at each clinic visit when the Haem-A-QoL, HAL and HLIQ are assessed. The 3 PGIC single item assessments will be also completed at each clinic visit when the Haem-A-QoL, HAL and HLIQ are assessed, but not at the baseline visit.

3.3.1.1. Hemophilia Life Impacts Questionnaire (HLIQ)

The HLIQ is a 9-item assessment of life impacts associated with living with and treating hemophilia. The HLIQ employs a 'past week' recall period. Four items are assessed on a 5-point, ordinal, verbal rating scale scored from 0 to 4, while 4 items are gated such that responding 'yes' branches to a 5-point, ordinal verbal rating scale and responding 'no' branches to a reason for not participating in the activity (i.e., due to hemophilia or due to

other reasons). One item is assessed on a 4-point, ordinal, verbal rating scale scored from 0 to 3. Higher scores on the verbal rating scales indicate greater impact due to living with or treating hemophilia.

HLIQ baseline is the latest evaluation prior to PF-07055480 infusion, which is measured during the baseline period of this study.

3.3.1.2. Patient Global Impression of Severity (PGIS) and Patient Global Impression of Change (PGIC)

The PGIS-Physical Health (PH) is a single item assessment of the participant's overall impression of severity of physical health over the past 7 days. The response scale is a 4-point categorical rating scale ranging from 'none' to 'severe'.

The PGIS-Physical Functioning (PF) is a single item assessment of the participant's overall impression of severity of physical functioning over the past 7 days. The response scale is a 4-point categorical rating scale ranging from 'none' to 'severe'.

The PGIS-Hemophilia (H) is a single item assessment of the participant's overall impression of severity of life interference with hemophilia over the past 7 days. The response scale is a 4-point categorical rating scale ranging from 'none' to 'severe'.

The PGIC-PH is a single item assessment of the participant's overall impression of change in their physical health since receiving gene therapy. The response scale is a 5-point categorical rating centered around 'no change' with 2 grades of improvement and 2 grades of worsening.

The PGIC-PF is a single item assessment of the participant's overall impression of change in their physical functioning since receiving gene therapy. The response scale is a 5-point categorical rating centered around 'no change' with 2 grades of improvement and 2 grades of worsening.

The PGIC-H is a single item assessment of the participant's overall impression of change in their life with hemophilia since being enrolled in the study. The response scale is a 5-point categorical response scale centered around 'no change' with 2 grades of improvement and 2 grades of worsening.

Data for PGIC and PGIS endpoints will be summarized with counts (%) by response for each visit.

3.3.1.3. EQ-5D-5L

Developed by the EuroQoL Group, the EQ-5D-5L (EuroQol, 5 dimensions, 5 levels) is considered the premier measure of health status used in the assessment of the Quality Adjusted Life Year. It measures 5 dimensions of health on a 5-point scale including Mobility, Self-care, Usual activities, Pain/discomfort, and Anxiety/depression.

Also included is a visual analog scale anchored by worst and best imaginable health on a 0 to 100 scale where participants are asked to indicate where on the scale, they rate their current health.

The value of 5 dimensions at each visit will be reported. The visual analogue scale (VAS) score and the Index score will be compared with baseline and summarized by visit. Details of the Index score are provided in [Section 6.3.1.3](#). Missing data will not be imputed, which means missing individual question responses will lead to missing dimension scores and total score. EQ-5D-5L baseline is the latest evaluation prior to PF-07055480 infusion, which is measured during the baseline period of this study.

3.3.2. Vector Shedding and Infectivity

Shedding will be assessed by quantitative real time polymerase chain reaction (PCR). Samples of plasma, saliva, PBMC, urine, and semen will be collected as specified in the SoA for analysis of vector shedding and infectivity. Peak values and the time to 3 consecutive specimens reaching the limit of quantification for each specimen type will be summarized.

Some participants (n=12), who consent to participate in an optional substudy, are expected to provide additional samples at early timepoints following study intervention (2 h [\pm 30 minutes], 24 h [\pm 3 h], 72 h [\pm 4 h] after completion of study intervention infusion and IV-line flush). This subset of samples will also be used for deoxyribonuclease (DNase) treatment for additional characterization. The data of this subgroup will be separately presented.

3.3.3. Pharmacodynamics

3.3.3.1. FVIII Antigen

Blood samples will be collected as specified in the SoA of the protocol and as specified in the Laboratory Manual to measure FVIII antigen levels. Any sample taken within 72 hours after administering standard half-life exogenous FVIII replacement therapy, or 120 hours for products with extended half-life, for any purpose (including treatment of bleeding or prevention purposes), will be excluded from summary or analysis. In addition, FVIII antigen data will be excluded after participants have resumed prophylaxis regimen.

3.3.3.2. Von Willebrand Factor

Von Willebrand factor levels will be measured. This factor is the transport protein for FVIII, and its levels may influence FVIII levels and activity.

Blood samples will be collected, prepared, and stored as specified in the SoA of the protocol and in the Laboratory Manual.

3.3.4. Joint Health Assessment

The following exploratory endpoints will be used to compare joint health post PF-07055480 infusion versus baseline:

- Number of target joints;
- Joint status as assessed by X-ray;
- Joint status as assessed by ultrasound.

The definition of target joints is provided [Section 3.2.7](#). Long-term joint outcomes will be based on the transition of participants to a mild hemophilia phenotype with maintenance of FVIII activity above the threshold to prevent joint bleeds supported by evidence of reduced target joint damage based on HJHS score and Pettersson score.

3.3.4.1. Ultrasound to Evaluate Joints

An ultrasound substudy will include a subset of participants (n~20) to undergo ultrasound exams to assess damage within joints by evaluating soft-tissue changes and osteochondral changes. The ultrasound scanning protocol will include data acquisition for both left and right sides of knees, elbows and ankles using the procedure and scoring method named Haemophilia Early Arthropathy Detection with Ultrasound (HEAD-US). Ultrasound scans will be acquired locally according to the SoA (i.e., at Screening or not later than Week4/Visit 6, Week 24, Week 52, or Early Discontinuation Visit) of the protocol.

HEAD-US is an additive scale for assessing severity of hypertrophic synovium and disease damage (in cartilage and bone separately) for each of the six joints. In addition, effusion (yes/no) will be recorded but not included in the score calculation.

3.3.4.2. X-ray Assessments to Evaluate Joints

Some participants (except for those participating in Germany) who consent to participate in an optional substudy, will undergo X-ray assessment for both left and right sides of knees, elbows, and ankles to assess damage within joints as detectable at a radiologic level. X-rays will be acquired according to the SoA (at Screening or not later than Week 4/Visit 6, Week 156, and Week 260 or Early Discontinuation Visit) of the protocol. All details of the X-ray acquisition will be captured in a separate scanning guide. At a minimum, joint images will be reviewed following the Pettersson scale. Central reading of X-ray images will be performed.

3.3.5. Effects on Coagulation

To evaluate for any effects on coagulation, the following assessments will be performed:

- Coagulation activation tests: aPTT, INR, D-dimer, TGA, TAT.
- Comparison of FVIII activity between one stage assay and chromogenic assay.
- Recovery of FVIII products post gene therapy.

3.3.6. Other Tertiary/Exploratory Endpoints

- Cellular immunity by cell-mediated assays.
- Binding IgG versus IgM assay.
- Other biomarkers as inflammatory cytokines.
- nAbs against other AAV serotypes.

- Endpoints in the optional liver biopsy substudy [including vector integration in the liver, histopathology assessment (e.g., presence of fibrosis assessment, presence of lymphocytic invasion), protein and/or RNA expression of FVIII and selected biomarkers (e.g., Grp78, Gal3BP)].

3.4. Baseline Variables

A baseline for each relevant endpoint is defined in the above corresponding section, as needed.

3.5. Safety Endpoints

The safety endpoints of this study include vital signs, AEs, serious AEs (SAEs), physical examinations, electrocardiograms (ECG), liver ultrasounds, immunogenicity, and laboratory tests.

3.5.1. Adverse Events

The definitions of an AE or SAE can be found in Protocol Appendix 3.

All ongoing AEs and SAEs in the lead-in study (C0371004), including events of special interest, as defined in the lead-in study (C0371004), will be collected as medical history for this study. Historical data on Medical, Surgical and Hemophilia History will be captured from the lead-in study. Any new AEs/SAEs after completion of the lead-in study will follow the AE reporting process (in Protocol Appendix 3).

The time period for actively eliciting and collecting AEs and SAEs ('active collection period') for each participant begins from the time the participant provides informed consent, which is obtained before the participant's participation in the study (i.e., before undergoing any study-related procedure and/or receiving investigational product), through and including a minimum of 5 years after the administration of the investigational product, or at End of Study (EOS) for participants who discontinue. The active collecting period for this study is categorized into short-term or long-term monitoring period and is defined later in this section.

For participants who are screen failures, the active collection period ends when screen failure status is determined.

Medical occurrences that begin before the start of study intervention but after obtaining informed consent will be recorded on the medical history/current medical conditions section of the case report form (CRF) not the AE section.

Follow up by the investigator continues throughout and after the active collection period and until the event or its sequelae resolve or stabilize at a level acceptable to the investigator, and Pfizer concurs with that assessment.

During the short-term monitoring period (up to and including 104 weeks postinfusion) all SAEs (including medically important events, described in Protocol Appendix 3) and AEs will be collected.

During the long-term monitoring period (Week 105 postinfusion to EOS) the following AEs will be collected:

- SAEs (including medically important events, Protocol Appendix 3).
- Nonserious AEs determined to be related to study intervention by the investigator or where causality is unknown.

Investigators are not obligated to actively seek AE or SAE after conclusion of the study participation. However, if the investigator learns of any SAE, including a death, at any time after a participant has been discharged from the study, and he/she considers the event to be reasonably related to the study intervention or study participation, the investigator must promptly notify the sponsor.

There is no lag time specified for reporting adverse events in this study. Treatment emergent adverse events (TEAEs) include any adverse events that occur on or after the start date of infusion of PF-07055480. TEAEs and SAEs will be summarized using the latest version of Medical Dictionary for Regulatory Activities (MedDRA) for the follow-up through data cutoff, the short-term monitoring period (up to and including 104 weeks postinfusion), and the long-term monitoring period (Week 105 postinfusion to EOS) separately.

3.5.2. Laboratory Data

Data from protocol-required safety laboratory assessments will be summarized by visit. These laboratory tests are provided in Protocol Appendix 2.

3.5.3. Physical Examinations

A complete physical examination will include, at a minimum, assessments of the cardiovascular, respiratory, gastrointestinal, and neurological systems. Height and weight will also be measured and recorded. Abnormal findings in physical examination will be summarized by MedDRA Preferred Term.

3.5.4. Vital Signs

Temperature (°C), pulse rate, respiratory rate, and blood pressure (systolic and diastolic) will be assessed after at least 5 minutes rest in supine or upright position.

3.5.5. Cardiac Monitoring

- Local single 12-lead ECG will be obtained using an ECG machine that automatically calculates the heart rate and measures PR, QRS and corrected QT intervals (QTc).
- Troponin I.

3.5.6. Liver Ultrasound

Liver surveillance by ultrasound (including hepatocellular carcinoma [HCC] detection) is planned as detailed in the SoA of the protocol.

3.5.7. Immunogenicity

The following immunogenicity assessments (listed in the table of protocol-required safety laboratory assessments) will be performed and reported:

- Analysis of Anti-PF-07055480 Antibodies and Neutralizing Anti PF-07055480 Antibodies.
- Analysis of FVIII Inhibitor; if there are two FVIII inhibitor results (one from assay with DOAC reversal agent and one without) at the same visit, the result with DOAC reversal agent should be used.
- Analysis of Cellular Immune Response against AAV6 capsid and transgene by Enzyme-Linked Immune-Spot (ELISPOT).

4. ANALYSIS SETS (POPULATIONS FOR ANALYSIS)

For purposes of analysis, the following populations are defined:

Population	Description	Applicable Analysis (for additional information refer to Section 6)
Enrolled	All participants who sign the informed consent form (ICF) and meet all inclusion/exclusion criteria.	Disposition events summary
Dosed/Safety	All participants enrolled in the study and who receive the study intervention.	Demographic and baseline characteristics, hemophilia history, medical history, safety, nAbs, ADA, FVIII antigen, von Willebrand factor, vector shedding assessments, joint health assessments, efficacy sensitivity/supplementary analyses, PRO analyses, and coagulation activation tests.
Evaluable	
All participants enrolled in the study and who receive the study intervention and have no significant interruption of efficacy measurement.
 
The ‘Evaluable’ analysis population will include participants who receive the study intervention (full dose of infusion) and exclude participants with significant interruption of efficacy measurement. The significant interruption would occur if the participant discontinues from the study, is lost to follow-up, has significant
	Efficacy sensitivity/supplementary analyses

Population	Description	Applicable Analysis (for additional information refer to Section 6)
	interruption in data collection, or has a major protocol deviation.	
Efficacy	All participants in the 'Dosed' population who have completed at least 6 months of follow up in the lead-in study and at least 15 months of follow up or discontinued from the study C3731003 prior to the data cutoff for reporting.	Main analysis population for efficacy
Ultrasound Substudy	All participants who sign the additional ICF for the ultrasound substudy and meet all inclusion/exclusion criteria, and the participant's joint ultrasound have been reviewed following the extended ultrasound scale at baseline, and any data post-baseline.	HEAD-US ultrasound scale - total score and subscores, demographic and baseline characteristics, AEs, disposition, and FVIII activity level data.
Vector Shedding Substudy	All participants who sign the additional ICF for the Vector Shedding substudy and meet all inclusion/exclusion criteria, and who provide any additional vector shedding data for analysis.	Shedding vector levels in PBMC, saliva, urine, semen, and plasma; demographic and baseline characteristics, AEs, disposition, and FVIII activity level data.
Joint X-Ray Substudy	All participants who sign the additional ICF for the optional joint x-ray substudy.	Joint status as assessed by X-ray in Pettersson scale.

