Global hemostasis markers and thrombophilia related markers (CL)		X*	X*	X*	
 ● See Appendix 2 for a full list of possible markers and Section 8.2.8 for more information. ● These samples should be collected in the absence of residual infused FVIII product (recommended washout is 72 h for standard half-life FVIII products and 120 h for extended half-life FVIII products). ● *Defined thrombophilia-related markers should be assessed at least once in each participant (if not initially assessed as part of eligibility confirmation) and some parameters can be repeated as clinically indicated, but are not repeated at each visit. ● Hemostasis markers should be assessed as clinically indicated throughout the study and are recommended to be tested if vector-derived FVIII:C >150% of normal are achieved .
HJHS		X	X	X	
To be completed by the investigator or the designee (Section 8.1.3.1).
 
Authorized time window: \pm1 month at W104 and \pm2 months at W156 and W208.

Procedures Year 2 to Year 5	Week 53- 104 (\pm 2 weeks)	Week 105-208- (\pm 3 weeks)	EOS or Early Discontinuation Week 260 (\pm 3 weeks)	
  Home health/mobile phlebotomy services may be used as needed (for most biological samples collection only).  Clinical decisions may be based on local or central laboratory assessments. 	
Study Visit	14	15	16	17	18
Weeks after study intervention	78	104	156	208	260
					If the HJHS cannot be performed at a visit, it is recommended that it be performed at the next subsequent on-site visit or unplanned visit.
PROs		X	X	X	
Participants will complete 6 instruments at the study site using an electronic tablet: Haem-A-QoL, HAL (v2), HLIQ, EQ-5D-5L, PGIS (n=3), PGIC (n=3). Administer the questionnaires before dosing, treatment, or conversation between the health care team and participants about their health condition. See Section 8.1.4 for additional considerations.
 
If PROs cannot be performed at a visit, it is recommended that it be performed at the next subsequent on-site visit or unplanned visit.

Phone call			Ongoing		After Week 156, phone calls every 6 months (ie, Weeks 182 and 234) in addition to the annual visits. Inquire about AEs and concomitant treatments (including surgeries).

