9.3. Populations for Analyses

For purposes of analysis, the following populations are defined:

Population	Description
Enrolled	All participants who sign the ICF and meet all inclusion/exclusion criteria.
Dosed/Safety	All participants enrolled in the study and who receive the study intervention.
Evaluable	All participants enrolled in the study and who receive the study intervention and have no significant interruption of efficacy measurement and no major protocol deviation.
Efficacy	All participants in the “Dosed” population who have completed at least 6 months in the lead-in study and at least 15 months of follow-up or discontinued from the study C3731003 prior to the data cutoff for reporting.

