9.4.2. Safety Analyses

All safety analyses will be performed on the Safety Population.

Endpoint	Statistical Analysis Methods
Primary	No primary safety endpoint.
Secondary	Descriptive analyses of SAE, AE of special interests, lab abnormality, etc. will be conducted.
Exploratory	Will be described in the SAP finalized before database lock.

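### Read literally, the Dosed/Safety set excludes anyone dosed and later found ineligible, because it is built on an Enrolled set that requires every eligibility criterion to be met

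*SAP*

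**What the plan says.** The table in SAP Section 4 defines the populations used for analysis. Its rows build on one another:

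- The first row, **Enrolled**, carries the eligibility condition: "All participants who sign the informed consent form (ICF) and meet all inclusion/exclusion criteria".
- The row for **Dosed/Safety** has no eligibility phrase of its own and relies on the word enrolled: "All participants enrolled in the study and who receive the study intervention".
- The **Evaluable** row starts from the same enrolled-and-treated group, requires a full dose, and gives a list of reasons for exclusion that ends with "interruption in data collection, or has a major protocol deviation".
- The main efficacy set, called **Efficacy**, is drawn from Dosed and is limited to "All participants in the 'Dosed' population who have completed at least 6 months of follow up in the lead-in study". A further condition covers follow-up or discontinuation in this study.

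Protocol Section 9.3 has the same Enrolled condition ("All participants who sign the ICF and meet all inclusion/exclusion criteria") and the same Dosed/Safety wording. Protocol Section 9.4.2 states: "All safety analyses will be performed on the Safety Population". SAP Section 6.6 says the same and adds that Safety and Dosed are one population.

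**The concern.** A safety population should contain everyone exposed. That matters especially here, because the vector is given once and cannot be withdrawn. If membership depends on meeting all criteria, a breach discovered after infusion takes an exposed participant out of the denominators and the event counts. Exclusions for thrombotic history, neoplasm or liver disease exist because such men are thought to be at higher risk of the matching events, so removing them would tend to make safety rates look better.

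The Dosed-set efficacy sensitivity analyses are meant to show the result in all treated participants, whatever their length of follow-up. They would instead become a selection made after dosing. In an open-label study, a decision taken later about how to read the word enrolled would be taken with outcomes known.

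**Working it through.** The plan states no figure on this point, so the check is one of set membership.

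**Definitions (SAP Section 4; Protocol Section 9.3)**

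1. Enrolled = consent signed AND all inclusion/exclusion criteria met.
2. Dosed = Safety = Enrolled AND received study intervention.
3. Evaluable is contained in (Enrolled AND received study intervention), less interruptions and major deviations.
4. Efficacy is contained in Dosed.

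**Test case.** Take a participant who received the vector and is later found to have failed one criterion. He fails step 1, so he is not in Enrolled. By step 2 he is not in Dosed/Safety, by step 3 not in Evaluable, and by step 4 not in Efficacy. The Ultrasound and Vector Shedding substudy rows repeat the eligibility condition, so he is outside those too. The Joint X-Ray Substudy row asks only for the substudy consent, so he could still appear there.

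**Analyses affected**

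| Analysis | Set | Includes him? |
|---|---|---|
| All safety tables (Protocol 9.4.2, SAP 6.6) | Safety = Dosed | No |
| Main Total ABR, FVIII activity above 5%, Treated ABR, AIR, FVIII consumption (SAP 6.1 to 6.2) | Efficacy | No |
| Efficacy sensitivity analyses and US-specific Total ABR (SAP 6.1 to 6.2, Appendix 1.4) | Dosed, Evaluable or Efficacy | No |
| HJHS, Haem-A-QoL, HAL, FVIII activity by visit | Dosed | No |
| Joint X-ray (exploratory) | Joint X-Ray Substudy | Yes, if he consented |

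**Is he restored anywhere?** No text in either document says that eligibility is taken as judged at enrolment, or that a dosed participant stays in Safety whatever is learned later. The protocol and SAP agree on these rows, so neither corrects the other.

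**Illustration of size.** The documents do not give the number affected. Assume all of the approximately 70 planned participants are dosed, and that the one man with a particular event is removed. Exact (Clopper-Pearson) 95% limits:

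- With him: 1/70 = 1.4%. Lower limit 1 − 0.975^(1/70) = 0.04%. The upper limit solves (1−p)^70 + 70p(1−p)^69 = 0.025, giving p = 7.7%.
- Without him: 0/69 = 0%. Upper limit 1 − 0.025^(1/69) = 5.2%.

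One removal would turn an observed event into none and lower the upper limit from 7.7% to 5.2%.

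**The case against.** The best defence is that enrolled in the Dosed/Safety row is an operational status. The Efficacy row names the Dosed population explicitly, whereas the Dosed/Safety row does not name the Enrolled population. Protocol Section 6.2 allows only enrolled participants to be dosed, Section 8 has eligibility reconfirmed on Day 1, and Section 5 bars waivers. On that view every dosed man is enrolled, and a breach found later is a protocol deviation. Listing major deviations as an exclusion only under Evaluable suggests that Dosed was meant to keep deviators. Protocol Sections 4.1 and 9.2 also use enrolled more broadly than eligible.

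All of this is plausible as intent, but none of it is written as a rule. The only definition of Enrolled given for analysis requires all criteria to be met.

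Four stronger inferences are tempting and are not supported:

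- **That the protocol itself produces ineligible dosed participants.** The Years 2 to 5 schedule says: "Defined thrombophilia-related markers should be assessed at least once in each participant (if not initially assessed as part of eligibility confirmation". The amendment history shows that the thrombophilia wording in exclusion 4 and the central tests came in together with Amendment 7, when participants had already been dosed. Late testing therefore fits catch-up in men enrolled under earlier criteria. It does not show a breach of the criteria that applied to them.
- **That the participant with the reported deep vein thrombosis would be dropped.** His risk factors are redacted, and nothing says that he breached a criterion.
- **That every analysis is affected.** The joint X-ray set is an exception.
- **That serious events would go unreported.** Individual AE and SAE recording and reporting do not depend on these sets. Only the tabulated analyses are affected.

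**Conclusion.** The point stands as a defect in the definitions. Applied as written, SAP Section 4 and Protocol Section 9.3 remove a dosed participant later found ineligible from all safety tables and from the main and Dosed efficacy analyses, and nothing puts him back. This rests on the literal reading. If the operational meaning was intended, the correction changes wording only.

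The documents identify no affected participant. If no breach is found after dosing, no result changes. The 1/70 against 0/69 contrast shows how sensitive a study of this size is to one removal and describes no known case. The definition should still be settled before it is applied, because it fixes who counts as exposed.

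**What to change.** Make matching changes in SAP Section 4 and Protocol Section 9.3:

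- **Dosed/Safety:** all participants who receive any amount of study intervention, regardless of eligibility findings.
- **Efficacy:** members of that set who received the complete infusion and meet the existing lead-in and follow-up (or discontinuation) conditions, regardless of eligibility findings. The complete-infusion limit is needed because Protocol Section 8, in its Day 1 text, keeps data from incomplete infusions out of efficacy analyses. Building Efficacy directly on an any-amount set would contradict that.
- **Dosed-set efficacy sensitivity analyses:** apply the same complete-infusion limit.
- **Evaluable:** keep this as the only set from which an eligibility breach is a reason for exclusion.

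The cost is a few lines of text in two documents and no new data. The downside for the sponsor is that reported safety rates may become slightly less favourable if such a participant exists.
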